### **3. Risks and Benefits**

This is a minimal risk study, and thus we do not anticipate problems beyond our control that involve risks to subjects and others happening.

No clinical assessments will be taken by research staff. Clinical data will be extracted from the EHR system at Piedmont as described above for evaluation and for participant study safety monitoring at 6, 12 and 24-month timepoints and will reflect their processes for routine screenings based on current clinical practice guidelines.

Physical activity: Risks from increased physical activity will be minimized by: 1) recommending physical activity in line with national guidelines; 2) encouraging moderate activity; and 3) directing participants to their physicians when appropriate. If exercise-related symptoms are reported, we will advise participants to get clearance from their PCPs before they can restart physical activity.

Participants will be counseled to change behaviors that will maintain or reduce weight. If individuals follow this advice and decide to change their health behaviors, there should be few risks or side effects. The materials and counseling will provide guidance on preventing and managing the side effects of health behavior change.

Data confidentiality: We will use the standard operating procedures that have been used on our prior trials for survey conduct and data management. All paper files related to the study will be stored in a secure location at Duke University in a locked file cabinet accessible only to key study personnel. The privacy, security, and durability of accumulated personal health information are of paramount importance.

Physical access to computing resources (hard drives, servers, networking equipment) is secure, audited, and restricted to skilled personnel; virtual access (login and system administration) is encrypted, audited, and limited to skilled personnel; all databases are encrypted and access from the public Internet is precluded; staff will be assigned unique login IDs and follow Duke standards for choosing passwords. We will also implement multifactor authentication to protect logins to databases. All communication between our software and third-party software is encrypted using SSL. Personnel must have access to perform regular maintenance duties. However, this constituency is limited to senior system administrators and the director of the research group. Surveys for enrollment, intervention goal assignment or intervention satisfaction will utilize Duke's secure HIPAA-compliant survey platform, Qualtrics and/or REDCap, that only authorized research staff can access. For the qualitative sub-study, verbal consent and participant information (name and assigned ID code number) will be stored within REDCap. Paper demographic surveys will contain the associated ID code number for the participant. Responses from the paper survey will be entered into the REDCap project that is linked to the participant after the interview. Original audio recordings will be transferred from the encrypted recorders to Duke Box for storage and then deleted from the recorders. Audio files will then be securely transferred to a HIPAA-compliant vendor to transcribe. When the transcripts are received from the vendor, they will be stored and accessed within Duke Box.

Prior to analyses in NVivo, participant names will be removed from the transcripts. Any written notes taken during the interviews will be securely stored in a locked file cabinet within a locked office and disposed of after analyses.

For the voluntary pragmatic design survey, we will utilize Duke Qualtrics to collect the survey data. The survey does not require participants to enter their names or other identifying information.

**Breach of confidentiality:** All participant information collected in the context of this study, and even the fact that an individual is participating in the study, will be considered confidential. Confidentiality will be assured through several mechanisms. First, each participant will be assigned an anonymous study ID that will be used on all study forms. Second, all study forms and paper records that contain participant information (e.g., HIPAA authorization forms) will be kept in secured, locked areas or in encrypted databases. In addition, such materials, when in use, will be kept away from public scrutiny. Materials that need to be discarded will be destroyed. Third, access to all participant data and information will be restricted to authorized personnel. In the case of computerized study data, access to data will be password-protected and staff members will be assigned individualized passwords that allow them access to only those elements of the data management system to which they are authorized. In addition, all study personnel will maintain certification with the Duke IRB that they have completed training in research ethics, which includes training on confidentiality. Finally, participants will not be identified by name in any reports or publications, nor will data be presented in such a way that the identity of individual participants can be inferred. All information obtained in the course of the study that identifies an individual will be treated as confidential in accordance with section 903C of the Public Health Service Act (42 U.S.C.299a-1). We will strip all identifiers from analytic data sets after data merging and will keep all personal identifiers in a separate location from the analytic data. No individual participant will be identified in any reports from the study. Data storage will involve computer files that will be password protected and encrypted and will be accessible only to personnel who need to contact participants.

In order to send and receive text messages, we will use a software engine that uses Twilio, Heroku, and Amazon S3. The engine will receive self-monitoring data that participants send via interactive voice response (IVR) and text message as well as weight data when they step on the BodyTrace scale. The data will be automatically analyzed each week according to algorithms we embed. Study staff will log into a password-protected database using multi-factor authentication to view and edit participant information. We will use Twilio to send text messages to participants each week. We will use Heroku to process data for the engine. We will use Amazon S3 to store data; data will be encrypted when it is stored. At times, we will transfer data from the engine to/from the participants and BodyTrace servers, and we will use Heroku and Twilio to do this. If data are disclosed by these companies or their business partners, it may no longer be covered under the Duke privacy protections. Text messaging does not provide a completely secure and confidential means of communication. Participants will be made aware of these risks as well as those that are inherent in using consumer-based products such as BodyTrace, telephone (IVR), and text messaging during the informed consent process. We used these processes on several previous studies conducted in this population.

**Potential Benefits:** Potential benefits for study participants include improved lifestyle, lower blood pressure and consequent reduction in cardiovascular risk. An additional benefit for some participants may be personal satisfaction in being part of a study that may have major public health implications for the community. No benefit from participation can be guaranteed. Potential benefits to others include the possibility that this research will lead to the dissemination of an intervention that can help maintain weight, with consequent reduction in the risks associated with diagnoses of diabetes, high cholesterol, and hypertension. Of particular importance is the fact that this project aims to provide an intervention in a culturally appropriate and sustained manner through use of intervention materials at an appropriate

reading level for the target population. The minimal health risks to participants listed above are offset by the potential benefits to them and to society.

#### **4. Confidentiality**

In the present study, we will collect identifying demographic information including: names, addresses, telephone numbers, and email addresses. We will use the standard operating procedures that have been used on our prior trials for survey conduct and data management. All paper files related to the study will be stored in a secure location at Duke University in a locked file cabinet accessible only to key study personnel and within a temporary lockbox or locked file drawer within an office at Piedmont Health (for HIPAA authorization forms that are in the clinic for the research assistant to pick up). The privacy, security, and durability of accumulated personal health information are of paramount importance. Physical access to computing resources (hard drives, servers, networking equipment) is secure, audited, and restricted to skilled personnel; virtual access (login and system administration) is encrypted, audited, and limited to skilled personnel; all databases are encrypted and access from the public Internet is precluded; staff will be assigned unique login IDs and follow Duke standards for choosing passwords. We will also implement multifactor authentication to protect logins to databases. All personnel must have access to perform regular maintenance duties. However, this constituency is limited to senior system administrators and the director of the research group.

Strategies for protecting electronic PHI: Study staff will enter all participant information into the study database, which is hosted and maintained in a remote data center. All software and servers are reachable only via logging in using multi-factor authentication and all communication between our software's application programming interface (API) and third-party software is encrypted using a protocol called Secure Sockets Layer (SSL). As described above, physical access to computing resources (hard drives, servers, networking equipment) is secure, audited, and restricted to skilled personnel; virtual access (login and system administration) is encrypted, audited, and limited to skilled personnel; all databases are encrypted and access from the public Internet is precluded; all software and servers are reachable only via a virtual private network (VPN) or multi-factor authentication; and all communication between our software's application programming interface (API) and third-party software is encrypted using SSL. In addition, Duke-provided HIPAA-compliant resources such as Qualtrics, REDCap and/or Duke Box may be used to collect and store research data for the study. Only research staff who have received CITI Certification and are listed on the Duke University Institutional Review Board protocol will have access to the study database. Information in the database will not be shared with anyone outside the research team.

On the study verbal consent script (Appendix A) and the Piedmont Health employee qualitative sub-study (Appendix P), we inform participants that we do collect identifying information and that we take all appropriate measures to minimize the risk of unintentional breach of confidentiality. In the Balance pragmatic design survey, we will inform participants about the potential loss of confidentiality and how we will mitigate those risks.

We will communicate with participants' providers at Piedmont Health about certain clinically relevant situations. We would communicate with providers for few reasons: 1) to obtain provider assent for patients with certain health conditions that do not make them ineligible, but that we are concerned about (example: mild cardiac condition); 2) to notify providers of situations we encounter during the regular course of the trial that are of particular concern to our staff. Examples of these situations include: participants with significant and dramatic weight loss or to discuss emergent, serious diagnoses in participants that may compromise their suitability for the trial. In clinically relevant situations, study staff will notify study participants of the concerning data (e.g. extreme weight loss) and advise them to follow

up with their providers according to the Data Safety Monitoring protocol. In addition, study staff will notify participants when there will be communication with their providers. Unless the clinical situation is serious and time-sensitive, we will communicate with Piedmont Health providers using “flags” in their EHR. The “flags” in Piedmont’s EHR system function as secure, internal emails. If the situation is clinically serious, we will contact the participant’s provider by phone. We have included information about this communication in the informed consent verbal script (Appendix A).

The information generated by this study will be kept for seven years after the date of last publication. Then it will be destroyed by shredding the paper copies and by securely deleting the computer files.

Data management will take place under the supervision of [name]. Our group has developed extensive quality assurance procedures, including on-going quality control checks.

After data analysis, we plan to disseminate the results of the study via journal publications and presentations.

We will not collect information about illegal activities. Further, we do not expect that participants will reveal information subject to reporting because our coaches are instructed to maintain close adherence to a protocol that involves discussing only behavior change efforts related to diet and exercise.

All of the same privacy measures and confidentiality procedures described above will also be adopted for the Balance satisfaction survey with patients and qualitative assessment with Piedmont Health employees. The online survey will be administered through Qualtrics. The qualitative assessment with Piedmont Health will be conducted in a private location (either in-person or on the phone). Collected survey and interview data and subsequent analyses will be stored within the Duke Box web application and/or REDCap that only authorized research staff at Duke will be able to access. To keep the Balance participants’ information private, we will use their study ID number and their Balance phone number only to identify their responses. To keep Piedmont Health employee responses confidential, we will remove names from interview transcripts, and identifying information linking their names to the code numbers on their interview and the demographic survey will be stored only within the restricted REDCap project.

## **5. Compensation**

Balance patient participants will not receive monetary compensation as part of their participation, as the baseline assessment will be brief and conducted primarily by phone. All participants, regardless of which program they are randomized to, will receive important health information/program materials as part of their participation as well as a pedometer. The main incentive for participation in this study (in either study arm) is to receive health information, materials and support for maintaining a healthy weight.

For the Balance satisfaction survey, to thank them for their time to take the survey (estimated to be 15-20 minutes), participants who decide to participate and complete the entire survey online will be compensated with a \$20 Amazon online gift card. The e-gift card will be texted or emailed to the participant, based on their preference. The incentive will be offered to mitigate the time burden involved with filling out the survey. Please see the attached script/process for the survey (Appendix M).

For the qualitative assessment, we will offer a \$25 Amazon online gift card to participating Piedmont Health employees in appreciation for their time (estimated to be 30-45 minutes). Similar to the satisfaction survey, the e-gift card will be texted or emailed to the participant, based on preference stated at the conclusion of the interview. (See Appendix P).

## **6. Informed Consent**

Please see the attached verbal consent script (Appendix A).

## **7. Deception**

Deception will not be used in the present study.

## **8. Debriefing**

We do not anticipate a need for debriefing.

## **STATISTICAL ANALYSIS PLAN**

## Statistical Analysis Plan

Baseline variables were summarized by the intervention arm as means and SDs for continuous variables and as counts and percentages for categorical variables. We used a 2-stage modeling strategy to answer our primary hypothesis. All analyses were intent-to-treat. For the first stage, we estimated the intervention effect on weight using a constrained longitudinal linear mixed effects model, using all available data from between 18 months pre-enrollment through 30.5 months postenrollment. We explored nonlinearities for the fixed effects of time and random effects of time in the models, guided by the Bayesian Information Criterion and likelihood ratio tests. The model included fixed effects for time and interactions between time segments and intervention, with a random intercept and random slopes for time. The covariance between random effects was modeled using an unstructured covariance matrix. Randomization was stratified by CHC; thus, we adjusted for CHC in the analyses but did not adjust for other variables. Using this linear mixed effects model, we estimated mean weight change by intervention arm, and the difference between intervention arms in mean weight change, at 6, 12, 18, and 24 months.

Second, we compared the percentage of  $\leq 3\%$  weight gain, our primary outcome, in each arm at 24- months postrandomization using individual empirical best linear unbiased predictors (EBLUPs) from the mixed model. To ensure good predictions, we only used individual EBLUPs from participants with at least 1 EHR weight documented within a 6-month window centered on the 24-month time point (ie, between 21 and 27 months postenrollment). We compared the percentage of  $\leq 3\%$  weight gain in intervention and usual care arms using both a log-binomial model and linear risk model on the EBLUP output, in order to obtain both risk ratios and risk differences, which provide estimates of relative and absolute efficacy, respectively. The extra variability induced by the EBLUPs being predicted from the model was taken into account using a resampling procedure, explained further in the Multimedia Appendices 1 and 2. Sensitivity to the 21- to 27-month window was assessed by obtaining predictions after expanding the window. We additionally used EBLUPs to compare the percentage of  $\leq 3\%$  weight gain in each arm at 6-, 12-, and 18-months postrandomization.

Additional sensitivity analyses included adjusting the model for baseline variables imbalanced across arms, by weight measured in the primary time window ( $P < .10$ ) and removing telehealth visits from the analysis. We also explored effect modification by adding interactions to the primary model with age tertiles; gender; BMI class; race and ethnicity; and preferred language (English or Spanish), each in a separate model. Additionally, in post hoc analyses we added the completion date of the study (pre- or post-COVID) as an effect modifier to examine the potential impact of COVID-19 on the intervention effect.

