Baseline Assessment: After receiving signed written HIPAA authorization form from a potential participant, to conduct the baseline screen/consent, Balance research staff will describe the study, determine eligibility for the study through a brief screen (See Appendix C), and if eligible and interested, obtain verbal consent, and administer a phone/in-person baseline survey. This will be conducted via phone or in-person in a private space at the clinic. A staff member will then randomly assign the participant to either Intervention or Usual Care arms. For those in the intervention arm, the staff member will deliver the iOTA survey, also by phone, in Spanish or English (see Appendix B for complete survey). The eligibility screen, verbal consent, and baseline survey will be administered via phone (in Spanish or English) or in-person, and entered into the Balance study database and within a secure platform such as Qualtrics and/or REDCap. Study surveys will eliminate or define medical terms, and use simple sentence structure and vocabulary.

Follow-up Data Collection: Given our pragmatic trial design, we will gather 12 to 18-month pre-randomization data, as well as 24 to 30-month follow-up data directly from Piedmont's EHR; we have a great deal of experience and well-established protocols in use. For each participant, we will assess the following data through 24 to 30 months following randomization: demographics (that were not asked at the baseline assessment including insurance status, poverty and marital status), and clinical data such as weight, blood pressure, smoking status, diagnostic codes, appointment dates, visit notes, lab tests (e.g. glucose and lipids), and medications. To receive the EHR follow-up data for evaluation purposes on enrolled Balance participants, we will utilize a Duke-provisioned Box folder to receive the data on enrolled participants from the Piedmont Health data manager/IT manager as follows:

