At Piedmont, weight and blood pressure are measured at all visits, including for acute care. Our proposed lab tests are also commonly administered. We will closely monitor patients' medical visits during the 24 to 30-month follow-up period. We have extensive experience retaining medically vulnerable patients, consistently reporting retention rates in the 90% range. We are thus confident that we will have adequate follow-up data to conduct our outcome analyses.

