## **2. Subject Selection**

**Inclusion Criteria:** The study involves males and females aged  $\geq 21$  years who are English and Spanish-speaking patients at a Piedmont Health Services primary care health center; and with a BMI between 25-40 kg/m^2 and weight less than 380 pounds. Eligible participants will have had a non-urgent visit to a Piedmont Health clinic within the last 2 weeks. Eligible participants will also have a cell phone and be willing to receive study-related text messages (3-12 messages per week).

**Exclusion Criteria:** Potential participants cannot: be a current Piedmont Health employee; currently or recently (within the past six months) pregnant or planning on becoming pregnant in the next 12 months; be currently or recently (past 2 months) lactating; have prior or planned bariatric surgery; have a diagnosis contraindicating weight loss (e.g., active malignancy); have a history of a cardiovascular event (stroke, MI); or have been hospitalized for a mental health issue in the last 12 months; have a diagnosis of end-stage kidney disease (ESRD) in the medical record; or due to investigator discretion for a potential health or safety issue. Potential participants who have a history of a coronary artery revascularization (in last 12 months) will be allowed to participate in the study with provider approval (See Appendix C).

**Sample size:** We will recruit up to 455 adult men and women, who speak either English or Spanish. At least 30% of the sample will be male (we recently recruited a 31% male sample in Track). The sample size calculation is based on the primary aim examining differences in the time to gain  $\geq 3\%$  of baseline weight between intervention and control groups. Based on Shape's clinical data, we assume a 5% sample loss for each group per month of the study. A sample of N=192 per group (Total N=384) allows us to test the difference between the two distributions with greater than 80% power. Factoring in an additional expected sample loss of 15% (those with no clinical data past baseline) gives a final sample size of N=221 per group (Total N=442, with the possibility of enrolling up to 455).

For the qualitative Balance implementation sub-study, we will recruit up to 25 Piedmont Health employees in varying roles and across the participating sites and leadership team.

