If eligible based on chart review, the Duke research assistant will then contact the patient via phone or in-person at the clinic. The patient will be screened, and if interested and still eligible to participate, will be verbally consented and enrolled, on the phone or in-person, by the research assistant. Trainings regarding the study purpose, directions about participant eligibility, intervention components, and processes to refer to the study will be conducted at participating Piedmont Health sites with involved staff.

2) Recruitment via Mail: To enhance our recruitment success and expand recruitment to other, more rural Piedmont Health clinic locations, we plan to reach out to potentially-eligible patients via mail in advance of their medical appointments. (Please also see Appendix J for the partial HIPAA authorization waiver). This will occur as follows:

Once or twice per month, Piedmont Health staff will run a report of all patients who are  $\geq 21$  years old; not currently pregnant; do not have end-stage renal disease, have a last recorded BMI and weight within our target range; speak English or Spanish as their primary language; and who have an upcoming medical appointment within the next 4-6 weeks at one of the participating Piedmont Health community health centers. The Piedmont report will be exported as a spreadsheet and securely sent (via their encrypted email system that they use to send sensitive emails/email that contains ePHI or via a restricted folder in within the Balance Duke Box folder) to the Balance study coordinator with the following information: patient name; gender (for letter salutation purposes); Date of Birth; mailing address; telephone number(s); email address; preferred language (Spanish/English); primary community health center; and upcoming appointment date. From this list, we would send a cover letter (See Appendix K); Balance study information (See Appendix F); and two copies of the HIPAA authorization form (See Appendix D) via postal mail. We would request that interested patients sign and return one copy of the form to us via mail to our office or printed, signed, scanned and returned as an attachment via email to our Duke Balance

email address. The patient would also have the option of returning the form to us during or immediately after their medical appointment at the clinic. The other copy of the HIPAA form would be for the patient to keep for his/her records.

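### Does the SAP need a rule for weights recorded during pregnancy?

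*Combined protocol and SAP*

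**What the plan says.** The Statistical Analysis Plan estimates weight trajectories in a mixed model "using all available data from between 18 months pre-enrollment through 30.5 months postenrollment". For the 24-month primary outcome, "we only used individual EBLUPs from participants with at least 1 EHR weight documented within a 6-month window centered on the 24-month time point". The protocol, under 1. Research Design, notes that "At Piedmont, weight and blood pressure are measured at all visits, including for acute care", so a visit for any reason can supply a weight.

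Pregnancy appears only at entry. In 2. Subject Selection the exclusion criteria bar anyone "currently or recently (within the past six months) pregnant or planning on becoming pregnant in the next 12 months", and the mailing list is limited to patients "not currently pregnant; do not have end-stage renal disease, have a last recorded BMI and weight within our target range". Section 4. Confidentiality provides for contact with providers about "emergent, serious diagnoses in participants that may compromise their suitability for the trial", which concerns patient care and not the choice of weights for analysis.

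The SAP's sensitivity analyses cover imbalanced baseline variables, telehealth visits and the window: "Sensitivity to the 21- to 27-month window was assessed by obtaining predictions after expanding the window". None concerns pregnancy. The EHR extract does include "clinical data such as weight, blood pressure, smoking status, diagnostic codes, appointment dates, visit notes", so pregnancies could be looked for.

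**The concern.** The trial measures failure to prevent weight gain. Gestational gain is a different thing, and the entry criteria treat pregnancy as incompatible with taking part. Yet once a participant is enrolled, the analysis as written cannot tell the two apart.

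The error could run both ways. Raised weights near month 24 could push a stable participant over 3%. Raised weights well before enrolment could lift the fitted starting weight and hide a real gain. All of the 21- to 27-month window is open to such weights, and up to 70% of the sample may be women. At stake would be the accuracy of each arm's success percentage and, if the error differed by arm, the primary comparison.

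**Working it through.** **1. Months open to pregnancy weights.** The data span is 18 + 30.5 = 48.5 months. The entry criterion closes months -6 to 0, and it screens intention for months 0 to 12. If that screen worked perfectly, the open time is (18 - 6) + (30.5 - 12) = 12 + 18.5 = 30.5 months, or 63%. Counting unplanned pregnancies in months 0 to 12 gives 42.5 months, or 88%. This is calendar time. It ignores men (at least 30% of the sample) and women past child-bearing age, so it does not show how often the problem occurs.

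**2. Denominator.** The protocol's 192 per group with 15% added is 192 × 1.15 = 220.8, or 221 per group (442 in total), as stated. About 2 × 192 = 384 are taken to have a weight in the window.

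**3. How many participants.** The documents give no pregnancy rate, so these inputs are assumptions. A pregnancy overlaps the 6-month window if conception falls in a period of 6 + 9 = 15 months. The expected number is 442 × share female × share of child-bearing age × yearly rate × 15/12:

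| Setting | Calculation | Participants |
|---|---|---|
| Low | 442 × 0.5 × 0.3 × 0.03 × 1.25 | 2.5 (0.6%) |
| Middle | 442 × 0.7 × 0.4 × 0.05 × 1.25 | 7.7 (1.8%) |
| High | 442 × 0.7 × 0.6 × 0.08 × 1.25 | 18.6 (4.2%) |

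**4. Whether one person crosses 3%.** Take a stable participant of 88 kg with nine other weights (assumed slope SD 1.5 to 3 kg/year, residual SD 1.5 to 2.5 kg). One window weight raised by 5 kg gives a predicted change of +1.8% to +2.1%, which does not cross. One raised by 10 kg gives +3.4% to +4.1%. Three raised by 3, 6 and 10 kg give +3.9% to +4.4%. Misclassification is therefore possible, but shrinkage limits it. Raised weights before enrolment move a prediction of +2.5% to +2.9% down to about -2%. In that example the class is the same either way, so it shows direction only.

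**5. Effect on the comparison.** The simulation used 221 per arm and 300 trials per setting. Assumed: 1%, 3% or 6% conceive in months 12 to 30.5; 1%, 2% or 4% deliver in months -18 to -6; peak gain 6 to 10 kg; true effect -2 kg at month 24. At 3% and 10 kg:

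| | No gestational gain | Weights kept | Weights excluded |
|---|---|---|---|
| Usual care success, % | 63.49 | 62.89 | 63.47 |
| Intervention success, % | 74.31 | 73.76 | 74.32 |
| Risk difference, points | 10.81 | 10.87 | 10.85 |
| Risk ratio | 1.170 | 1.173 | 1.171 |
| Window set | 383.8 | 383.8 | 376.8 |

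The binomial standard error with weights kept (191.9 per arm) is √[(0.6289 × 0.3711 + 0.7376 × 0.2624)/191.9] = 4.72 points. After exclusion (188.4 per arm) it is 4.74. Total misclassified is 18.79 people with no gestational gain and 20.74 with weights kept, an excess of 1.95; most of the error comes from the prediction step itself. Across all settings the excess is 0.4 to 4.3 people and the risk difference shifts by -0.04 to +0.12 points.

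**6. A ceiling that does not depend on the simulated variances.** Suppose 6% of each arm has a pregnancy after month 12 and every success among them is turned into a failure. Success becomes 63.49 × 0.94 = 59.68 and 74.31 × 0.94 = 69.85. The risk difference is 10.17, a fall of 0.65 points from 74.31 - 63.49 = 10.82, or about 0.14 standard errors. The risk ratio is unchanged at 1.170, because both arms shrink by the same factor.

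**7. What exclusion costs.** It removes about 2, 7 or 14 of 384 from the window set at 1%, 3% or 6%. At 3%, about 0.03 × 384 = 11.5 have a pregnancy after month 12, so a loss of 7.0 is about 60% of them. Only about 19% of those with such a pregnancy were misclassified in the first place.

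**The case for a change.** The best case for a change is that the outcome should mean what it says. A gestational gain counted as failed prevention is a measurement error with a known cause, and the fields needed to look for it are already extracted. The SAP already removes telehealth visits in a sensitivity analysis, so a similar step for pregnancy would fit. The loss of participants could be reduced with the expanded window, or avoided by predicting from their other weights. A reader may reasonably ask how many were affected.

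Part of this stands. The SAP is silent, each arm's success percentage could be slightly low, and a count of affected participants would be informative. The simulated share of misclassified participants among those with a pregnancy after month 12 (12% to 21%) is also less certain than it looks. Slope SD, residual SD and number of visits were held fixed and are not in the documents; varying them gives about 11% to 36%.

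None of this reaches the comparison. The ceiling in step 6 allows for complete misclassification and still moves the risk difference by well under one point. The remedy is not free either. It departs from using all data under intent-to-treat, and it changes the target to weight outside pregnancy. It also needs pregnancies dated from codes and notes, since no conception or delivery dates are listed among the extracted fields.

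**Conclusion.** The SAP has no rule for weights recorded in pregnancy, and some such weights could enter the model. No change is needed. Pregnancy should occur about equally in the two randomised arms, so the expected shift is -0.04 to +0.12 points in a risk difference with a standard error near 4.7, and almost nothing in the risk ratio. Each arm's success percentage may be 0.1 to 1.3 points low. Exclusion gains no precision and removes more participants (about 2 to 14) than the misclassification it addresses (0.4 to 4.3). Keeping all weights is a fair choice for an intent-to-treat pragmatic trial, and analysts can describe affected records from the codes and notes they hold without altering the plan.

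These sizes rest on assumed pregnancy rates, gains, variances and visit counts, none of which the documents give. The conclusion itself needs less: pregnancy about equally common in the two arms, and affecting no more than a few percent of the analysed participants. The appendices and the Data Safety Monitoring protocol mentioned in section 4 were not available and may already contain a rule.
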